**5. Annexure – E: Budget**

## **ANNEXURE - A**

### **Application for Ethical Clearance**

**Title of the study:** Spatiotemporal gait parameters of healthy and stroke patients during overground, self-paced treadmill, and body-weight supported treadmill walking.

**Co-Principal Investigator(s):**

[name]

Department of Physical Medicine and Rehabilitation, Dhaka Medical College Hospital (DMCH), Dhaka-1205, Bangladesh.

**Place of the Study/Institution(s):** Biomechanics and biofluid lab, Department of Biomedical Engineering (BME), BUET, Dhaka - 1000, Bangladesh.

**Type of Study:** Comparative study.

**Duration of Study:** 6 months

**Total Cost:** 30,000 Tk.

**Funding Agency:** N/A.

**Circle the appropriate answer to each of the following**

**(If not Applicable write NA)**

**1. Source of Population:**

(a) Ill Participant       Yes       No  
(b) Non Ill Participant       Yes       No  
(c) Minors or persons under guardianship       Yes       No

(a) Nature and purposes of study       Yes       No

(b) Procedures to be followed including alternatives used       Yes       No

(c) Physical risks       Yes       No

**2. Does the study involve?**

(a) Physical risks To the subjects       Yes       No  
(b) Social Risks       Yes       No  
(c) Psychological Risks to subjects       Yes       No  
(d) Discomfort to Subjects       Yes       No  
(e) Invasion of the body       Yes       No  
(f) Invasion of Privacy       Yes       No  
(g) Disclosure of Information damaging to Subject or others       Yes       No

(d) Private questions       N/A

(e) Invasion of the Body       N/A

(f) Benefits to be Derived       Yes       No

(g) Right to refuse to participate or to withdraw from study       Yes       No

(h) Confidential handling of data       Yes       No

(i) Compensation where there are risks or loss of working time or privacy is involved in any particular procedure       N/A

**3. Does the study involve?**

(a) Use of records, (Hospital, medical, Death, birth or other)       Yes       No  
(b) Use of fetal tissue Or abortus       Yes       No  
(c) Use of organ or Body fluids       Yes       No

**5. Will signed consent form/verbal consent be required?**

(a) From Subjects       Yes       No  
(b) From parent or guardian (if subjects are minors)       N/A

**4. Are subjects clearly informed about?**

**6. Will precautions be taken to protect anonymity of subjects**       Yes       No

***Note: If the final instrument / questionnaire is not completed prior to review, the following information should be included in the abstract.***

1. A description of the areas to be covered in the questionnaire or interview which could be considered either sensitive or which would constitute an invasion of privacy.
2. Examples of the type of specific question to be asked in the sensitive areas.
3. An indication as to whom the questionnaire will be presented to the committee for review.

---

**We agree to obtain approval of the Ethical Review Committee for any changes involving the rights and welfare of subjects or any changes of the Methodology before making any such changes.**

---

**Date: 20/08/2024**

**Name of Co-investigator (S)**

**Signature**

**\* Include all the Investigator, Co-Investigators.**

**ANNEXURE - B**  
**ABSTRACT FOR**  
**BME Ethical Review Committee (BMEERC)**

The Ethical Review Committee will not consider any application which does not include a specific abstract/summary for the committee. The abstract should summarize the study's purpose, the methods, and procedures to be used by addressing each of the following items. If an item is not applicable, please note accordingly:

1. Describe the requirements in respect of the population and explain the rationale for using the population of special groups such as children, Incompetent person, or groups whose ability to give voluntary informed consent is questionable.

**Response:** The primary aim of the study is to evaluate the differences in variability in spatiotemporal gait parameters of stroke patients during overground, self-paced treadmill, and body-weight supported treadmill walking. Stroke, while more common in older adults, can affect people of all ages. As a result, our study participants range in age from 18 to 75 years, allowing us to better understand the impact of stroke across a larger age range. Children under the age of 18 and individuals who are unable to provide voluntary informed consent will be given consent from a parent or legally authorized guardian. Furthermore, consent will be obtained from children who are old enough to understand the study, ensuring that they are willing to participate. Pregnant women are not allowed to participate in the study due to safety concerns. The specific inclusion criteria are listed below:

*Post-stroke patients who are able to walk and aged between 18 to 75 (not pregnant).*

2. Describe and assess any potential risks - physical, psychological, social, legal or other and assess the likelihood and seriousness of such risks. If methods of research create potential risks, describe other methods, if any, that were considered and why they cannot be used.

**Response:** The primary aim of the study is to compare the variability in spatiotemporal gait parameters of stroke patients across overground, self-paced treadmill, and body-weight supported treadmill walking, and to identify which walking technique yields the most consistent and beneficial gait metrics, indicating a more stable and effective recovery. If the post-stroke subject is afraid of falling, an overhead harness will be used to ensure their safety during data collection.

The use of the body weight support structure (BWSS), which is designed to help participants with balance issues, carries minimal physical risk. The structure can support up to 5 tons and has been tested on healthy adults weighing an average of 80 kg for up to 4 minutes. The overhead harness is intended to provide comfort by evenly distributing pressure across the lumbar and thoracic regions, and it includes a thigh belt for added safety. There may be some psychological discomfort due to unfamiliarity with the

equipment or the testing environment. There are no anticipated social or legal risks in this study.

3. Describe procedures for protecting against or minimizing potential risks and assessment of their likely effectiveness.

**Response:** The study is designed to minimize potential risks through careful planning and implementation of safety measures. The primary risk mitigation strategy involves using a body weight support structure during data collection for stroke subjects. This structure can support up to 5 tons and has been tested for safety and comfort. It includes an overhead harness to provide support during walking. During the data collection process, participants will be continuously monitored by the study investigators. Any signs of physical discomfort, fatigue, or deterioration in condition will result in the immediate termination of the experimental trial. Participants unable to walk with the overhead harness or express discomfort will not be subjected to the experiment.

4. Include a description of the methods for safeguarding confidentiality or protecting anonymity.

**Response:** The study will implement strict protocols to safeguard the confidentiality and anonymity of participants. All collected data will be accessible only to authorized study personnel. Personal identifying information will be removed from the data after the study is completed. Each participant will be assigned a unique code, and only coded data will be used in the analysis and reporting of study results.

5. When there are potential risks to the subject, or the privacy of the individual may be involved, the investigator is required to obtain a signed informed consent from the participant. For minors, informed consent must be obtained from the authorized legal guardian or parent of the subject. Describe consent procedures to be followed, including how and where informed consent will be obtained.

- (a) If signed consent will not be obtained, explain why this requirement should be waived and provide an alternative procedure such as a verbal consent.

**Response:** Informed consent will be obtained.

- (b) If information is to be withheld from a subject, justify this course of action.

**Response:** No information will be withheld from the subject.

- (c) If there is a potential risk to the subject or privacy of the individual or loss of work time is involved in any particular procedure, include a statement in the consent form stating whether any compensation will be available.

**Response:** Not applicable since there is a minimal risk of privacy and loss of work time.

6. If the study involves an interview, describe where and in what context the interview will take place. State approximate length of time required for the interview.

**Response:** The study will not require an interview.

7. Assess the potential benefit to be gained by the individual subject as well as the benefits which may accrue to society in general because of the work. Indicate how the benefits may outweigh the risks.

**Response:** The study offers potential benefits to individual subjects and society, which outweigh the minimal risks associated with participation. After conducting the experiment, each participant will receive a gait analysis report. Especially, in the case of post-stroke patients, the gait impairment can be evaluated by this report. Again, In Bangladesh, there is a scarcity of gait analysis facilities. Moreover, the study could serve as a foundation for further research in gait analysis within Bangladesh that may inform and enhance therapeutic practices, leading to better treatment and rehabilitation strategies for post-stroke patients. In the long run, the establishment of gait analysis research can have a significant public health impact, improving the quality of care for individuals with gait abnormalities. The potential risks associated with the study are minimal and include minor physical discomfort or fatigue during the gait analysis.

8. In case of an experimental drugs, provide information about its status of registration for open sale in Bangladesh and in other developed countries.

**Response:** N/A.

9. For experimental 'new' drugs\* which are not registered in Bangladesh provide full information about the toxicity studies carried out in animals or human volunteers. Published papers on this regard shall be annexed.

**Response:** N/A.

10. If placebo is to be used justify its uses and why the study cannot be done without its use.

**Response:** N/A.

11. If an experimental 'new' drug\* is to be used give a statement regarding its sponsorship and the conditions for such sponsorship.

**Response:** N/A.

12. State if the activity requires the use of records (hospital, medical, birth, death or other), organs, tissues, body fluids, the fetus or the abortus.

**Response:** Yes. The study will require the use of medical records, including stroke type, the duration since the stroke occurred, paretic side by stroke, hospital admission and release dates etc.

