### **Summary:**

This study aims to collect and analyze spatiotemporal data from stroke patients using an in-house gait analysis setup. Each walking modality-overground, self-paced treadmill, and body-weight supported treadmill provides distinct advantages and challenges. Overground walking simulates natural conditions but lacks mechanical support; self-paced treadmill walking provides a controlled environment with adjustable speed; and body-weight supported treadmill walking reduces lower extremity pressure and the risk of falling. A locally made body weight support structure (BWSS) is used for fall prevention in hemiparetic patients during data collection. The BWSS includes: Hand winch system with locking mechanism, Double pulley system, An overhead harness, and A 10 ft Stainless steel wire (loading capacity=5 ton). For Overground, data collection is done using two force plates positioned in the middle of a linear pathway, an 8-camera video monitoring system, and AcqKnowledge software is used for data analysis. Data collection from the self-paced treadmill and body-weight supported treadmill also occur through the video monitoring system. Data collection will adhere to standard protocols to ensure safety and accuracy. Participants will walk along the pathway, and gait data will be recorded using the force plates and video system. By analyzing gait parameters such as step length, stride length, cadence, gait speed, and the duration of stance and swing phases, the study aims to identify which modality offers the most consistent and stable gait patterns, indicating improved motor control and coordination.

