### **Objectives:**

In this study, we aim to evaluate the gait differences among three different walking modalities with respect to spatiotemporal gait parameters. This will be achieved through a comparative analysis of spatiotemporal data between those groups. To ensure the safety of the subjects, the data collection protocols will be strictly followed, incorporating already tested procedures that have shown no probable risk. The BWSS has been tested with healthy individuals and is manufactured using widely available components in Bangladesh. The objectives of the study are as follows:

- **Study objectives:** To evaluate the variations in spatiotemporal gait parameters of three different walking modalities and analyze and determine which walking technique provides the most reliable gait metrics, suggesting a more stable and possibly advantageous recovery outcome.
- **Study Hypothesis:** We hypothesize that body weight supported treadmill walking will exhibit the least variability in spatiotemporal gait parameters compared to overground walking and self-paced treadmill walking. This suggests that BWST provides a more controlled environment, promoting more consistent and reliable gait patterns, which may translate to a more stable and potentially advantageous recovery outcome for individuals with stroke.

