### **Rationale:**

Stroke is a leading cause of disability worldwide, significantly impairing mobility and increasing the risk of falls. In Bangladesh, stroke is not only a major health concern due to its high prevalence and mortality rate but also has a substantial economic impact, with a large number of disability-adjusted life years lost. Despite the high incidence of stroke and the resultant gait impairments, there is a significant gap in the availability of gait analysis in Bangladesh. Most existing studies in

the region rely on traditional, observational methods that often provide inaccurate data and focus primarily on spatiotemporal parameters, neglecting crucial biomechanical insights.

Gait analysis, which measures characteristics such as stride length, step time, and swing time (spatiotemporal parameters), is critical for evaluating gait quality and monitoring rehabilitation progress. Overground walking analysis is widely regarded as the gold standard [8]. However, environmental factors such as uneven surfaces, obstacles, and a fear of falling can cause data variability [9]. Treadmill walking provides a controlled environment and facilitates data collection, but the question remains: which environment yields the most reliable and informative data for post-stroke gait assessment and rehabilitation planning?

This study fills this knowledge gap by investigating the variability of spatiotemporal gait parameters across three walking environments:

- Overground walking: Represents real-world walking but can be influenced by environmental factors, as previously stated.
- Self-paced treadmill walking provides a controlled environment, but may not fully challenge balance and coordination, potentially yielding less informative data on these aspects of gait.
- Body weight supported treadmill walking (BWST): Provides partial support, potentially promoting more consistent gait patterns due to lower balance demands, which may be beneficial for initial gait training.

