Understanding the variability of gait parameters across these environments is important for several reasons. Identifying the environment that produces the most consistent and reliable gait data enables researchers and clinicians to select the best assessment method for post-stroke patients. This can result in more accurate assessments of gait impairments and progress during rehabilitation. Therapists can tailor gait training programs to specific environments based on rehabilitation objectives and individual needs. For example, because of its supportive nature, BWST may be a useful tool for initial training, whereas overground walking practice becomes more critical as balance and coordination improve. Additionally, it will provide a reliable and safe method for gait analysis that can be widely adopted in Bangladeshi healthcare setting and lay the groundwork for future research and clinical applications in gait analysis and rehabilitation for stroke patients in Bangladesh. Ultimately, this study seeks to improve the assessment and management of gait impairments in stroke patients, contributing to better rehabilitation outcomes and enhancing the quality of life for affected individuals.

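### Annexure B never names a fall as a study risk, and no fall or stopped walk is recorded, so the Rationale's safety claim has no planned data from stroke patients

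*Protocol*

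**What the plan says.** **Risks stated to the committee.** The Protocol's Annexure B, item 2 asks for all potential risks with their likelihood and seriousness. The response calls the physical risk of the support structure minimal and adds: "There may be some psychological discomfort due to unfamiliarity with the" equipment or the test setting. Item 7, on benefits against risks, says: "The potential risks associated with the study are minimal and include minor physical discomfort or fatigue during the gait analysis".

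**Falling, as it appears elsewhere.** The item 2 response also says: "If the post-stroke subject is afraid of falling, an overhead harness will be used to ensure their safety during data collection". In Annexure C, the Summary states: "A locally made body weight support structure (BWSS) is used for fall prevention in hemiparetic patients during data collection". The Rationale describes stroke as "significantly impairing mobility and increasing the risk of falls".

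**Basis for calling the procedures safe.** The Objectives speak of "incorporating already tested procedures that have shown no probable risk" and say that the structure was tested with healthy people. Item 2 describes that test: healthy adults, mean weight 80 kg, for up to 4 minutes. It gives no number of people tested and no results.

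**Stopping and recording.** Item 3 provides for continuous monitoring, and for ending the walk when discomfort, tiredness or worsening is seen. Table 1 lists gait and ground-reaction outcomes, with force-plate and video data collected during walking. The Case Report Form has 42 items on demographics, history, clinical scales, gait parameters and functional tests.

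**What is promised.** The Rationale says of the study that "it will provide a reliable and safe method for gait analysis that can be widely adopted in Bangladeshi healthcare setting".

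**The concern.** The protocol describes a safeguard against falls without listing the fall it guards against. A committee weighing risk under items 2 and 7 therefore gets no assessment of how likely or how serious a fall is. The population gives reason to ask: patients from just over one month after stroke are eligible, including those who walk with assistance.

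Two things are at stake for inference. First, the Rationale attaches the word safe to the method, but the study as laid out would end without a fall count or a stopping count in stroke patients. Second, the hypothesis ranks three modalities by gait variability. If less steady walks are the ones stopped early, and nothing records which were stopped and in which modality, their loss cannot be seen when modalities are compared. A modality could then look steadier than it is.

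**Working it through.** The plan gives no safety figure to reproduce, so the main check sets its sections side by side.

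| Question | Where checked | Result |
|---|---|---|
| Is a fall named as a study risk, with likelihood and seriousness? | Annexure B, items 2, 3 and 7 | No. Psychological discomfort, minor physical discomfort and fatigue are named. |
| Does the protocol recognise falling? | Item 2; Summary; Introduction; Rationale | Yes, through the harness, the purpose of the structure, the effect of weight support and the effect of stroke. |
| Can a walk be ended early? | Item 3 | Yes. |
| Is a fall, near-fall, harness catch or stopped walk an outcome or a planned data item? | Table 1 | No. |
| Is there a field for any of these? | Case Report Form, items 1 to 42 | No. The nearest items are assistive device, Timed Up and Go and the 10-metre walk. |
| Is safety of the method asserted as a product of the study? | Rationale | Yes. |
| Is prior safety evidence in stroke patients described? | Item 2; Objectives | No. Only healthy people are mentioned. |

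The second row conflicts with the first, the third with the fourth and fifth, and the sixth with the fourth, fifth and seventh.

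**What recording could show.** The number of subjects, n = 25, comes from the sample size section and Table 1. Formula (i) with SD 0.3, difference 0.17 and k = 3 gives 2 × 0.3² × (0.84 + 1.96)² / (0.17² × 2) = 24.4. This agrees with the stated 24 before the dropout allowance; the present point does not depend on it.

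Exact upper 95% limit for the per-patient risk after 0 events in n:

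- two-sided: 1 − 0.025^(1/25) = 0.137, or 13.7%
- one-sided: 1 − 0.05^(1/25) = 0.113, or 11.3%

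After 1 event in 25, the exact (Clopper-Pearson) two-sided interval is 0.1% to 20.4%.

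The chance of seeing at least one event in 25 patients is 1 − (1 − p)^25. The documents give no event rate, so p is assumed:

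| Assumed per-patient risk p | Chance of at least one event |
|---|---|
| 1% | 22% |
| 2% | 40% |
| 5% | 72% |
| 10% | 93% |

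These figures do not measure the defect. They show how far a safety statement could go if the events were counted.

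**The case against.** The strongest reply is that the committee does have the hazard in front of it. Falling is mentioned within item 2 itself, item 3 makes the support structure the main mitigation, and Annexure C states its purpose plainly. The item 7 sentence is worded as inclusive rather than exhaustive, and can be read as the risk left after mitigation. This stands in part: the committee is not kept in the dark. It does not supply what item 2 asks for, which is a fall named as a risk with its likelihood and seriousness.

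The reply continues that safety is neither an objective, an outcome nor a planned analysis, and that the disputed phrase is one sentence of Rationale about future use. This also stands, and it makes the point minor. The sentence is still written as something the study will deliver.

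Four stronger readings are tempting, and the documents do not support them:

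- **Participants are not told of the fall risk.** The consent form is not among the pages available, so what it says about falls is unknown. The answers circled on the application form for physical risk are not legible either.
- **Not one safety observation is made.** Investigators watch every participant and cameras film the walks. A fall would probably be on video; what is missing is any step to extract or count it.
- **The study would report a formal safety finding.** No planned analysis produces one.
- **The procedures were tested only in healthy people.** That is the only testing described, but the study is headed as a third, extended phase and the earlier phases are not set out here. The basis is undocumented, not shown to be absent.

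It is also fair to say that counts from 25 patients would hardly separate the modalities. That argues for descriptive reporting, not for leaving the events unrecorded.

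**Conclusion.** The point holds as a minor one. The protocol recognises falling and guards against it, but does not list or assess it as a study risk. It allows walks to be ended, but has no field to record that they were. It attaches safety to the method without planning to collect evidence in stroke patients.

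The primary outcome, gait velocity, and its tests are unaffected, except that early-stopped walks would go unseen by modality. That this could favour one modality assumes that stopped walks tend to be the less steady ones, which is plausible but not established in the document.

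Even with complete recording, no events in 25 patients would exclude only per-patient risks above roughly 11% to 14%, depending on whether the limit is one- or two-sided. The conclusion rests on Table 1 and the Case Report Form as shown, not on anything that a separate analysis plan would be expected to hold.

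**What to change.** 1. **Reconcile the risk text.** Name falls as a foreseeable risk in Annexure B, items 2 and 7, with likelihood and seriousness as item 2 requires. Bring these into line with the Summary, Objectives and Rationale. In the Objectives, state what testing supports the assurance and in whom. Check that the participant information, not seen here, agrees.
2. **Add fields to the Case Report Form for each modality.** Tick-boxes would cover fall, near-fall or harness catch, and walk stopped early with the reason. The form as shown has one set of gait entries and no modality label, so the new lines should name the modality.
3. **Report the counts.** Give them by modality, descriptively, with exact intervals, and show stopped walks alongside the gait comparison.
4. **Limit or withdraw the word safe in the Rationale,** so that it claims no more than those counts support.

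The cost is a wording change to the submission, a less favourable risk statement and slightly more recording by investigators who already monitor every walk. No clinical rule needs to change: the existing harness and stopping provisions are only to be described consistently and their use recorded.
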